8.5. Deaths

If any patient dies during the study, all relevant information will be discussed in the patient's narrative included in the CSR.

8.6. Vital Signs

Summary statistics for vital signs (pulse, systolic and diastolic blood pressure, and respiratory rate) will be presented at baseline, and the end of treatment and ET visits. Vital signs values and changes from baseline to each visit will be summarized using descriptive statistics.

Summaries of potentially clinically significant abnormal values will include all postbaseline values (including scheduled, unscheduled, and early termination visits). The incidence of potentially clinically significant abnormal values will be summarized using descriptive statistics with the criteria specified in [Table 2](#).

[Table 2](#) specifies the criteria for identifying vital signs as potentially clinically significant abnormal values. Note that in order to qualify as potentially clinically significant abnormal, a value needs to meet both criteria below: ie, have a value beyond the criterion value and a change of at least the magnitude specified in the change relative to baseline column.

Table 2: Criteria for Potentially Clinically Significant Vital Signs

Vital Sign	Criterion value	Change relative to baseline
Pulse	≥ 120 bpm	Increase of ≥ 15 bpm
	≤ 50 bpm	Decrease of ≥ 15 bpm
Systolic blood pressure	≥ 180 mm Hg	Increase of ≥ 20 mm Hg
	≤ 90 mm Hg	Decrease of ≥ 20 mm Hg
Diastolic blood pressure	≥ 105 mm Hg	Increase of ≥ 15 mm Hg
	≤ 50 mm Hg	Decrease of ≥ 15 mm Hg
Respiratory rate	<10 breaths/min	

8.7. Concomitant Medications or Therapies

Concomitant medications and therapies, including medications that are taken on an as needed basis and occasional therapies, will be monitored during the study. Details of prohibited medications may be found in Section 5.6 of the study protocol. All concomitant medications will be coded using the WHO drug.

The incidence of concomitant medications and therapies will be summarized using descriptive statistics by therapeutic class category and preferred term. The incidence of concomitant medications for asthma at baseline will also be summarized using descriptive statistics by therapeutic class category and preferred term. Patients are counted only once in each therapeutic class, and only once in each preferred term category. Concomitant medications will include all medications taken from the day of treatment start through the end of treatment.

9. TOLERABILITY VARIABLES AND ANALYSIS

Tolerability is not applicable to this study.

10. STATISTICAL SOFTWARE

All data listings, summaries, and statistical analyses will be generated using SAS® version 9.4 or later.

11. CHANGES TO ANALYSES SPECIFIED IN THE STUDY PROTOCOL

The definition of the mITT analysis set (see Section 3.1.2) has been updated to include patients with at least 1 postbaseline ACT assessment rather than including patients with at least 1 postbaseline assessment on any of the study endpoints.

The analysis for the primary endpoint (see Section 6.2.2) has been updated to allow for different response rates at enrolling investigational centers.

Patients who discontinue treatment due to an adverse event related to IMP will be considered a nonresponder in the analysis for the primary endpoint (see Section 6.2.2) and in the sensitivity analyses (see Section 6.2.3).

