9.2.2. Modified Intent-to-Treat Analysis Set

The modified intent-to-treat (mITT) analysis set is a subset of the ITT analysis set including only patients who receive at least 1 dose of IMP (IMP is either FS eMDPI or Albuterol eMDPI for the DS group or SoC medication for the SoC group) and at least 1 postbaseline assessment on any of the study endpoints.

In the mITT analysis set, treatment will be assigned based on the treatment to which patients were randomized, regardless of which treatment they actually received. This analysis will be used for all primary, secondary, endpoint analyses.

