3.1.2. Modified Intent-to-Treat Analysis Set

The modified intent-to-treat (mITT) analysis set is a subset of the ITT analysis set including only patients who receive at least 1 dose of IMP (IMP is either FS eMDPI or Albuterol eMDPI for the DS group or SoC medication for the SoC group) and at least 1 postbaseline ACT assessment.

In the mITT analysis set, treatment will be assigned based on the treatment to which patients were randomized, regardless of which treatment they actually received. This analysis set will be used for all primary, secondary, [REDACTED] endpoint analyses.

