6. DATA ANALYSIS

6.1. General

The efficacy of the drug product will not be evaluated in this study. The focus of this study is the engagement of the patient with the FS eMDPI DS and Albuterol eMDPI DS.

The mITT analysis sets will be used for all data analyses, unless otherwise specified. Summaries will be presented by treatment group, as randomized.

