6.3.3. Secondary Endpoint #3 – Adherence to Maintenance Treatment**6.3.3.1. Definition**

Secondary endpoint #3 is the change from baseline in adherence to maintenance treatment (FS eMDPI), defined as the proportion of actual inhalation doses taken out of the total number of inhalation doses prescribed over the 24-week treatment period. Daily adherence to maintenance treatment will be defined as $100 * (\text{number of inhalations}/2)$ if number of inhalations ≤ 2 (ie, for number of inhalations = 0, 1 and 2). Daily adherence to maintenance treatment will be defined as 100% if number of inhalations > 2 .

Weekly adherence to maintenance treatment will be defined as total daily adherence in 7 days/7. Monthly adherence to maintenance treatment will be defined as total daily adherence in 28 days/28.

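### The postbaseline-ACT condition on the mITT set drops some early leavers from secondary endpoints #1 to #3, none of which is derived from a postbaseline ACT

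*SAP*

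**What the plan says.** The operative text is SAP 3.1.2. To enter the mITT set a randomised patient needs one dose of IMP "and at least 1 postbaseline ACT assessment". The same section adds: "This analysis set will be used for all primary, secondary" endpoints. SAP 6.1 makes this the default: "The mITT analysis sets will be used for all data analyses, unless otherwise specified". SAP 6.3.1 to 6.3.3 name no other set for endpoints #1 to #3.

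Protocol 9.2.2 was wider. After the dose condition it asked only for "at least 1 postbaseline assessment on any of the study endpoints". SAP 11 lists the narrowing as a change, saying that the definition "has been updated to include patients with at least 1 postbaseline ACT assessment rather than including patients with at least 1 postbaseline assessment" on any endpoint, and gives no reason.

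The three endpoints draw on other data. Endpoint #1 counts provider interventions, which are recorded at Visits 2 and 3 and also at any Clinically Driven Assessment (SAP 2.1). Endpoint #2 is built from weekly inhalation counts. Endpoint #3 is "defined as the proportion of actual inhalation doses taken out of the total number of inhalation doses prescribed", scored day by day from the inhaler. Endpoints #2 and #3 concern the DS group only.

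**The concern.** A set defined by the ACT suits an ACT analysis. Applied to endpoints that do not use the ACT, it removes patients because an unrelated measure is missing. It also does so selectively, because having a postbaseline ACT depends on staying to Week 12 or attending an ET visit.

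Protocol 4.3 requires withdrawal for noncompliance with study procedures or with either inhaler, and for use of other SABA products. Poor adherence and unusual SABA behaviour are therefore among the reasons for leaving, and those who leave without an ACT vanish from the adherence and SABA summaries. SAP 6.1 names patient engagement with the Digital System as the study's focus, and these two endpoints measure it most directly.

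Endpoint #1 is compared between arms in a Bayesian Poisson model (SAP 6.3.1.2). Some discontinuation reasons, such as disliking the DS, can arise only in the DS arm, so the loss could differ by arm.

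**Working it through.** **Step 1. Who is excluded.**

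- Protocol Table 5 and section 6.1.1: after baseline, the ACT is given at Visit 2 (Week 12), Visit 3 or an ET visit. Before Week 12 only an ET visit can supply one, and there it is given in person.
- Protocol 4.3: early termination assessments are made where possible. SAP 4.3 has a rule for leavers with no ET visit, so such patients are expected.
- Protocol 5.1.2.1 and 5.1.2.2: inhaler data pass to the App and then to the cloud without a visit.

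A treated patient with neither a Visit 2 nor an ET ACT can thus hold inhaler or intervention records, satisfy Protocol 9.2.2 through them, and still fail SAP 3.1.2. The Poisson model for #1 contains a covariate y0. The SAP does not define it there, but in the primary model it is the baseline ACT. A baseline value does not justify a postbaseline condition.

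**Step 2. The plan's own figure.** Protocol 9.1 and SAP 2.4: 350 evaluable patients with 10% dropout. 350 / 0.90 = 388.9, against the stated 388. This agrees to within one patient.

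**Step 3. How many patients.** With 4:3 allocation, DS = 388 × 4/7 = 221.7 and SoC = 388 × 3/7 = 166.3. Ten per cent dropout (assumed equal in both arms) gives 22.2 DS and 16.6 SoC, 38.8 in all. The documents do not say what share f of leavers has no postbaseline ACT, so f is an assumption:

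| f | DS lost (#2, #3) | SoC lost | All lost (#1) | Fraction q |
|---|---|---|---|---|
| 0% | 0 | 0 | 0 | 0% |
| 25% | 5.5 | 4.2 | 9.7 | 2.5% |
| 50% | 11.1 | 8.3 | 19.4 | 5% |
| 100% | 22.2 | 16.6 | 38.8 | 10% |

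**Step 4. Effect on mean adherence in Week 1.** The mean over all treated patients is (1 − q) × kept + q × excluded. Hence the mean of those kept, minus the mean of all, is q × (kept − excluded). The documents give no adherence values. I assume gaps of 20 and 40 points, for example 70% against 50% or 30%:

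| q | Gap 20 | Gap 40 |
|---|---|---|
| 0% | 0 | 0 |
| 2.5% | 0.5 | 1.0 |
| 5% | 1.0 | 2.0 |
| 10% | 2.0 | 4.0 |

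Week 1 is the maximum for a given gap, because the excluded patients then leave one by one. Once they have gone they have no later weeks to contribute, so later summaries are the same under either definition.

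As a reference case, suppose dropout is even over 24 weeks. About half the leavers then go before Week 12. If none of these has an ET ACT, q is about 5% and the shift is 1 to 2 points. If half of them do, q is about 2.5% and the shift is 0.5 to 1 point.

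No comparable sum is possible for SABA use or for the intervention rates, since the documents give no values to work from.

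**The case against.** The change is disclosed, and the SAP states that it prevails over the protocol. Endpoints #2 and #3 are descriptive and confined to one arm, so no comparison rests on them. All of this stands, and it limits the weight of the point without giving a reason for the rule.

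Device data may be incomplete. Transfer needs the App and an internet connection; otherwise the data are downloaded from collected inhalers (Protocol 5.2.3), and someone who skips the ET visit may not return them. A reader might infer that every excluded patient has a complete record up to departure. The documents do not support that: some will have partial data or none.

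The remedy does not cure later attrition. Weeks 12 to 24 still rest on those who stayed. Done carelessly, it could also harm #2: SAP 6.3.2.1 scores a week without inhalations as zero use and 7 SABA-free days, and SAP 4.1 lets treatment end default to last contact. An unsynchronised or departed patient could then appear SABA-free. That is correct, and the fix has to deal with it.

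A reader might also treat the differing denominators of the safety-set inhalation tables (SAP 8.2 and 8.3) and the mITT tables as a defect. Safety and efficacy sets often differ, and the fix creates differing denominators of its own, so I do not rely on this.

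**Conclusion.** The point holds, as a modest one that is cheap to correct. SAP 3.1.2 excludes from endpoints #1 to #3 treated patients who have neither a Visit 2 nor an ET ACT, and the protocol's wording would have kept those with endpoint records.

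Two broader readings are tempting. One is that every secondary endpoint is affected; but #7 (safety) is analysed on the safety set. The other is that all early leavers are lost; but anyone with a Visit 2 or an ET ACT stays in.

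The size is not known and starts at zero: 0 to about 22 of 222 DS patients for #2 and #3, and 0 to about 39 of 388 for #1. The upper ends require every planned dropout to leave without a postbaseline ACT. The likely direction for adherence is upward, by 0 to at most 4 points in Week 1 under the assumed gaps, shrinking afterwards. A definite bias of several points throughout the early weeks is not shown. The direction for SABA use and the effect on the between-arm comparison in #1 are undetermined.

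**What to change.** In SAP 3.1.2, with a matching entry in SAP 11, limit the postbaseline-ACT condition to the ACT analyses in SAP 6.2. For endpoints #1 to #3, include randomised patients with at least one dose and at least one postbaseline record on that endpoint.

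- **#1:** the record is follow-up time together with any interventions in it, so a patient with none contributes a zero count. The model's existing logt term, apparently log follow-up time, allows for short follow-up.
- **#2 and #3:** count only up to the end of treatment or the last device transmission, whichever is earlier, so that the no-inhalation rule in SAP 6.3.2.1 does not score unobserved weeks as SABA-free.

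The cost is one revised definition, a second population flag, and denominators that differ between ACT and non-ACT tables, which a footnote can explain. No new data are needed. Non-use after the last transmission stays unobserved, and attrition in later weeks remains; the footnote should say both.
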